### **Reporting of AE, SAE, and Other Reportable Safety Events to the Sponsor**

AE, SAE, and Other Reportable Safety Event Reporting to Sponsor via Electronic Data Collection Tool

• The primary mechanism for reporting to the Sponsor will be the electronic data collection (EDC) tool.

• Electronic reporting procedures can be found in the EDC data entry guidelines (or equivalent).

• If the electronic system is unavailable for more than 24 hours, then the site will use the paper AE Reporting form.

• Reference section 9.3.1 – Time Period and Frequency for Collecting AE and SAE and Other Reportable Safety Event Information for reporting time requirements

• The site will enter the SAE data into the electronic system as soon as it becomes available.

• After the study is completed at a given site, the electronic data collection tool will be taken off-line to prevent the entry of new data or changes to existing data.

- If a site receives a report of a new SAE from a study participant or receives updated data on a previously reported SAE after the electronic data collection tool has been taken off-line, then the site can report this information on a paper SAE form or by telephone (see next section).
- Contacts for SAE reporting can be found in the Investigator Trial File Binder (or equivalent).

#### **SAE Reporting to the Sponsor via Paper CRF**

- If the electronic data collection tool is not operational, facsimile transmission or secure e-mail of the SAE paper CRF is the preferred method to transmit this information to the Sponsor.
- In rare circumstances and in the absence of facsimile equipment, notification by telephone is acceptable with a copy of the SAE data collection tool sent by overnight mail or courier service.
- Initial notification via telephone does not replace the need for the investigator to complete and sign the SAE CRF pages within the designated reporting time frames.
- Contacts and instructions for SAE reporting and paper reporting procedures can be found in the Investigator Trial File Binder (or equivalent).

## **12.5 Appendix 5: Contraceptive Guidance and Pregnancy Testing**

### **Definitions**

#### **Woman of Childbearing Potential (WOCBP)**

A woman is considered fertile following menarche and until becoming postmenopausal unless permanently sterile (see below)

Women in the following categories are not considered WOCBP:

- Premenarchal
- Premenopausal female with 1 of the following:
  - Documented hysterectomy
  - Documented bilateral salpingectomy
  - Documented bilateral oophorectomy

Note: Documentation can come from the site personnel's review of the participant's medical records, medical examination, or medical history interview.

- Postmenopausal female
  - A postmenopausal state is defined as no menses for 12 months without an alternative medical cause.
    - A high follicle stimulating hormone (FSH) level in the postmenopausal range may be used to confirm a postmenopausal state in women not using hormonal contraception or hormonal replacement therapy (HRT). However, in the absence of 12 months of amenorrhea, confirmation with two FSH measurements in the postmenopausal range is required.
  - Females on HRT and whose menopausal status is in doubt will be required to use one of the non-hormonal highly effective contraception methods if they wish to continue their HRT during the study. Otherwise, they must discontinue HRT to allow confirmation of postmenopausal status before study enrollment.

## **Contraception Requirements**

### **Male Participants**

Male participants with female partners of childbearing potential are eligible to participate if they agree to one of the following during the protocol-defined time frame in section 6.1:

- Be abstinent from penile-vaginal intercourse as their usual and preferred lifestyle (abstinent on a long-term and persistent basis) and agree to remain abstinent.
- Use a male condom plus partner use of an additional contraceptive method when having penile-vaginal intercourse with a woman of childbearing potential who is not currently pregnant.
  - The following are not acceptable methods of contraception:
    - Periodic abstinence (calendar, symptothermal, post-ovulation methods), withdrawal (coitus interruptus), spermicides only, and lactational amenorrhoea method (LAM).
    - Male condom with cap, diaphragm or sponge with spermicide.
    - Male and female condom cannot be used together.
  - Note: Men with a pregnant or breastfeeding partner must agree to remain abstinent from penile-vaginal intercourse or use a male condom during each episode of penile penetration.

### **Female Participants**

Female participants of childbearing potential are eligible to participate if they agree to consistent and correct use of a highly effective method of contraception as described in [Table 14](#) during the protocol-defined time frame in Section 6.1.

Table 14 Highly Effective Contraceptive Methods

Highly Effective Contraceptive Methods That Are User Dependent a  Failure rate of <1% per year when used consistently and correctly.

Combined (estrogen- and progestogen- containing) hormonal contraception b, c
 
 
○ Oral a, b (with additional barrier method for participants on lenvatinib treatment)
 
○ Intravaginal
 
○ Transdermal
 
○ Injectable
 

Highly Effective Methods That Have Low User Dependency  Failure rate of <1% per year when used consistently and correctly.

 
● Progestogen- only contraceptive implant b, c
 
● Intrauterine hormone-releasing system (IUS) c
 
● Intrauterine device (IUD)
 
● Bilateral tubal occlusion
 

 
● Vasectomized partner  A vasectomized partner is a highly effective contraception method provided that the partner is the sole male sexual partner of the WOCBP, and the absence of sperm has been confirmed. If not, an additional highly effective method of contraception should be used.
 

 
● Sexual abstinence  Sexual abstinence is considered a highly effective method only if defined as refraining from heterosexual intercourse during the entire period of risk associated with the study treatment. The reliability of sexual abstinence needs to be evaluated in relation to the duration of the study and the preferred and usual lifestyle of the participant.
 


Notes:
 
Use should be consistent with local regulations regarding the use of contraceptive methods for participants of clinical studies.
 
 
a) Must be on a stable dose of the same oral hormonal contraceptive product for at least 4 weeks before dosing with study drug and for the duration of the study.
 
b) If locally required, in accordance with Clinical Trial Facilitation Group (CTFG) guidelines, acceptable contraceptive implants are limited to those which inhibit ovulation.
 
c) If hormonal contraception efficacy is potentially decreased due to interaction with study treatment, condoms must be used in addition to the hormonal contraception during the treatment period and for at least 120 days after the last dose of study treatment.
 

### **Pregnancy Testing**

WOCBP should be included only after a negative highly sensitive urine or serum pregnancy test within 24 hours of the first dose. If urine pregnancy results cannot be confirmed as negative, a serum pregnancy test will be required. Monthly pregnancy testing should be conducted as per local regulations where applicable. For lenvatinib arm, following initiation of treatment, additional pregnancy testing will be performed as indicated in Section 2 during the treatment period and at least every 30 days up to 120 days after the last dose of study medication or the start of a new anticancer therapy, whichever comes first.

Following initiation of treatment, pregnancy testing will be performed whenever an expected menstrual cycle is missed or when pregnancy is otherwise suspected and as required locally.

## **12.6 Appendix 6: Collection and Management of Specimens for Future Biomedical Research**

### **1. Definitions**

- a. Biomarker: A biological molecule found in blood, other body fluids, or tissues that is a sign of a normal or abnormal process or of a condition or disease. A biomarker may be used to see how well the body responds to a treatment for a disease or condition.
- b. Pharmacogenomics: The investigation of variations of DNA and RNA characteristics as related to drug/vaccine response.
- c. Pharmacogenetics: A subset of pharmacogenomics, pharmacogenetics is the influence of variations in DNA sequence on drug/vaccine response.
- d. DNA: Deoxyribonucleic acid.
- e. RNA: Ribonucleic acid.

### **2. Scope of Future Biomedical Research**

The specimens consented and/or collected in this trial as outlined in Section 9.8 – Future Biomedical Research Samples will be used in various experiments to understand:

- o The biology of how drugs/vaccines work
- o Biomarkers responsible for how a drug/vaccine enters and is removed by the body
- o Other pathways drugs/vaccines may interact with
- o The biology of disease

The specimen(s) may be used for future assay development and/or drug/vaccine development.

It is now well recognized that information obtained from studying and testing clinical specimens offers unique opportunities to enhance our understanding of how individuals respond to drugs/vaccines, enhance our understanding of human disease and ultimately improve public health through development of novel treatments targeted to populations with the greatest need. All specimens will be used by the Sponsor or those working for or with the Sponsor.

### **3. Summary of Procedures for Future Biomedical Research**

#### **a. Participants for Enrollment**

All enrolled in the clinical study will be considered for enrollment in future biomedical research.

#### **b. Informed Consent**

Informed consent for specimens (ie, DNA, RNA, protein, etc.) will be obtained during screening for protocol enrollment from all participants or legal guardians, at a trial visit by the investigator or his or her designate. Informed consent for Future Biomedical Research should be presented to the participants on the visit designated in the SoA. If delayed, present consent at next possible Participant Visit. Consent

forms signed by the participant will be kept at the clinical trial site under secure storage for regulatory reasons.

A template of each trial site's approved informed consent will be stored in the Sponsor's clinical document repository.

**c. eCRF Documentation for Future Biomedical Research Specimens**

Documentation of participant consent for Future Biomedical Research will be captured in the electronic Case Report Forms (eCRFs). Any specimens for which such an informed consent cannot be verified will be destroyed.

**d. Future Biomedical Research Specimen(s)**

Collection of specimens for Future Biomedical Research will be performed as outlined in the SoA. In general, if additional blood specimens are being collected for Future Biomedical Research, these will usually be obtained at a time when the participant is having blood drawn for other trial purposes.

**4. Confidential Participant Information for Future Biomedical Research**

In order to optimize the research that can be conducted with Future Biomedical Research specimens, it is critical to link participant's clinical information with future test results. In fact little or no research can be conducted without connecting the clinical trial data to the specimen. The clinical data allow specific analyses to be conducted. Knowing participant characteristics like gender, age, medical history and treatment outcomes are critical to understanding clinical context of analytical results.

To maintain privacy of information collected from specimens obtained for Future Biomedical Research, the Sponsor has developed secure policies and procedures. All specimens will be single-coded per ICH E15 guidelines as described below.

At the clinical trial site, unique codes will be placed on the Future Biomedical Research specimens. This code is a random number which does not contain any personally identifying information embedded within it. The link (or key) between participant identifiers and this unique code will be held at the trial site. No personal identifiers will appear on the specimen tube.

**5. Biorepository Specimen Usage**

Specimens obtained for the Sponsor will be used for analyses using good scientific practices. Analyses using the future biomedical research specimens may be performed by the Sponsor, or an additional third party (eg, a university investigator) designated by the Sponsor. The investigator conducting the analysis will follow the Sponsor's privacy and confidentiality requirements. Any contracted third party analyses will conform to the specific scope of analysis outlined in future biomedical research protocol and consent. Future biomedical research specimens remaining with the third party after specific analysis is performed will be reported to the Sponsor.

**6. Withdrawal From Future Biomedical Research**

Participants may withdraw their consent for Future Biomedical Research and ask that their biospecimens not be used for Future Biomedical Research. Participants may withdraw consent at any time by contacting the principal investigator for the main trial. If

medical records for the main trial are still available, the investigator will contact the Sponsor using the designated mailbox ([contact]). Subsequently, the participant's specimens will be flagged in the biorepository and restricted to main study use only. If specimens were collected from study participants specifically for Future Biomedical Research, these specimens will be removed from the biorepository and destroyed. Documentation will be sent to the investigator confirming withdrawal and/or destruction, if applicable. It is the responsibility of the investigator to inform the participant of completion of the withdrawal and/or destruction, if applicable. Any analyses in progress at the time of request for withdrawal/destruction or already performed prior to the request being received by the Sponsor will continue to be used as part of the overall research trial data and results. No new analyses would be generated after the request is received.

In the event that the medical records for the main trial are no longer available (eg, if the investigator is no longer required by regulatory authorities to retain the main trial records) or the specimens have been completely anonymized, there will no longer be a link between the participant's personal information and their specimens. In this situation, the request for withdrawal of consent and/or destruction cannot be processed.

#### **7. Retention of Specimens**

Future Biomedical Research specimens will be stored in the biorepository for potential analysis for up to 20 years from the end of the main study. Specimens may be stored for longer if a regulatory or governmental authority has active questions that are being answered. In this special circumstance, specimens will be stored until these questions have been adequately addressed.

Specimens from the trial site will be shipped to a central laboratory and then shipped to the Sponsor-designated biorepository. If a central laboratory is not utilized in a particular trial, the trial site will ship directly to the Sponsor-designated biorepository. The specimens will be stored under strict supervision in a limited access facility which operates to assure the integrity of the specimens. Specimens will be destroyed according to Sponsor policies and procedures and this destruction will be documented in the biorepository database.

#### **8. Data Security**

Databases containing specimen information and test results are accessible only to the authorized Sponsor representatives and the designated trial administrator research personnel and/or collaborators. Database user authentication is highly secure, and is accomplished using network security policies and practices based on international standards to protect against unauthorized access.

#### **9. Reporting of Future Biomedical Research Data to Participants**

No information obtained from exploratory laboratory studies will be reported to the participant, family, or physicians. Principle reasons not to inform or return results to the participant include: Lack of relevance to participant health, limitations of predictive capability, and concerns regarding misinterpretation.

If important research findings are discovered, the Sponsor may publish results, present results in national meetings, and make results accessible on a public website in order to

rapidly report this information to doctors and participants. Participants will not be identified by name in any published reports about this study or in any other scientific publication or presentation.

#### **10. Future Biomedical Research Study Population**

Every effort will be made to recruit all participants diagnosed and treated on Sponsor clinical trials for Future Biomedical Research.

#### **11. Risks Versus Benefits of Future Biomedical Research**

For future biomedical research, risks to the participant have been minimized. Risks include those associated with venipuncture to obtain the whole blood specimen. This specimen will be obtained at the time of routine blood specimens drawn in the main study.

The Sponsor has developed strict security, policies and procedures to address participant data privacy concerns. Data privacy risks are largely limited to rare situations involving possible breach of confidentiality. In this highly unlikely situation there is risk that the information, like all medical information, may be misused.

#### **12. Questions**

Any questions related to the future biomedical research should be e-mailed directly to [[contact]](mailto:[contact]).

## **12.7 Appendix 7: Country-specific Requirements**

### **12.7.1 Spain-specific, United Kingdom-specific, and Italy-specific Requirement**

Pregnancy testing in WOCP is to be done monthly during the treatment period.

### **12.7.2 Ireland-specific Requirement**

Pregnancy testing in WOCP is to be done monthly during the treatment period.

Hepatitis B and hepatitis C testing should be performed at Screening.

### **12.7.3 Russia-specific Requirement**

Hepatitis B, hepatitis C and HIV testing should be performed at Screening.

### **12.7.4 South Africa-specific Requirement**

HIV testing should be performed at Screening.

## 12.8 Appendix 8: Description of the iRECIST Process for Assessment of Disease Progression

### *Assessment at Screening and Prior to RECIST 1.1 Progression*

Until radiographic disease progression based on RECIST 1.1, there is no distinct iRECIST assessment.

### *Assessment and Decision at RECIST 1.1 Progression*

For participants who show evidence of radiological PD by RECIST 1.1 as determined by the investigator; the investigator will decide whether to continue a participant on study treatment until repeat imaging is obtained (using iRECIST for participant management; see [Table 9](#) and [Figure 3](#)). This decision by the investigator should be based on the participant's overall clinical condition.

Clinical stability is defined as the following:

- Absence of symptoms and signs indicating clinically significant progression of disease
- No decline in ECOG performance status
- No requirements for intensified management, including increased analgesia, radiation, or other palliative care

Any participant deemed **clinically unstable** should be discontinued from study treatment at site-assessed first radiologic evidence of PD and is not required to have repeat tumor imaging for confirmation of PD by iRECIST.

If the investigator decides to continue treatment, the participant may continue to receive study treatment and the tumor assessment should be repeated 4 to 8 weeks later to confirm PD by iRECIST, per investigator assessment. Images should continue to be sent to the central imaging vendor for potential retrospective use.

Tumor flare may manifest as any factor causing radiographic progression per RECIST 1.1, including:

- Increase in the sum of diameters of target lesion(s) identified at baseline to  $\geq 20\%$  and  $\geq 5$  mm from nadir
  - o Note: the iRECIST publication uses the terminology “sum of measurements”, but “sum of diameters” will be used in this protocol, consistent with the original RECIST 1.1 terminology.
- Unequivocal progression of non-target lesion(s) identified at baseline
- Development of new lesion(s)

iRECIST defines new response categories, including iUPD (unconfirmed progressive disease) and iCPD (confirmed progressive disease). For purposes of iRECIST assessment, the first visit showing progression according to RECIST 1.1 will be assigned a visit (overall) response of iUPD, regardless of which factors caused the progression.

At this visit, target and non-target lesions identified at baseline by RECIST 1.1 will be assessed as usual.

New lesions will be classified as measurable or non-measurable, using the same size thresholds and rules as for baseline lesion assessment in RECIST 1.1. From measurable new lesions, up to 5 lesions total (up to 2 per organ), may be selected as New Lesions – Target. The sum of diameters of these lesions will be calculated and kept distinct from the sum of diameters for target lesions at baseline. All other new lesions will be followed qualitatively as New Lesions – Non-target.

*Assessment at the Confirmatory Imaging*

On the confirmatory imaging, the participant will be classified as progression confirmed (with an overall response of iCPD), or as showing persistent unconfirmed progression (with an overall response of iUPD), or as showing disease stability or response (iSD/iPR/iCR).

*Confirmation of Progression*

Progression is considered confirmed, and the overall response will be iCPD, if ANY of the following occurs:

- Any of the factors that were the basis for the initial iUPD show worsening
  - o For target lesions, worsening is a further increase in the sum of diameters of  $\geq 5$  mm, compared to any prior iUPD time point
  - o For non-target lesions, worsening is any significant growth in lesions overall, compared to a prior iUPD time point; this does not have to meet the “unequivocal” standard of RECIST 1.1
  - o For new lesions, worsening is any of these:
    - An increase in the new lesion sum of diameters by  $\geq 5$  mm from a prior iUPD time point
    - Visible growth of new non-target lesions
    - The appearance of additional new lesions
- Any new factor appears that would have triggered PD by RECIST 1.1

*Persistent iUPD*

Progression is considered not confirmed, and the overall response remains iUPD, if:

- None of the progression-confirming factors identified above occurs AND
- The target lesion sum of diameters (initial target lesions) remains above the initial PD threshold (by RECIST 1.1)

Additional imaging for confirmation should be scheduled 4 to 8 weeks from the imaging on which iUPD is seen. This may correspond to the next visit in the original visit schedule. The assessment of the subsequent confirmation imaging proceeds in an identical manner, with possible outcomes of iCPD, iUPD, and iSD/iPR/iCR.

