### *Resolution of iUPD*

Progression is considered not confirmed, and the overall response becomes iSD/iPR/iCR, if:

- None of the progression-confirming factors identified above occurs, AND
- The target lesion sum of diameters (initial target lesions) is not above the initial PD threshold.

The response is classified as iSD or iPR (depending on the sum of diameters of the target lesions), or iCR if all lesions resolve.

In this case, the initial iUPD is considered to be pseudo-progression, and the level of suspicion for progression is “reset”. This means that the next visit that shows radiographic progression, whenever it occurs, is again classified as iUPD by iRECIST, and the confirmation process is repeated before a response of iCPD can be assigned.

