### *Detection of Progression at Visits after Pseudo-progression Resolves*

After resolution of pseudo-progression (ie, achievement of iSD/iPR/iCR), iUPD is indicated by any of the following events:

- Target lesions
  - o Sum of diameters reaches the PD threshold ( $\geq 20\%$  and  $\geq 5$  mm increase from nadir) either for the first time, or after resolution of previous pseudo-progression. The nadir is always the smallest sum of diameters seen during the entire study, either before or after an instance of pseudo-progression.
- Non-target lesions
  - o If non-target lesions have never shown unequivocal progression, their doing so for the first-time results in iUPD.
  - o If non-target lesions have shown previous unequivocal progression, and this progression has not resolved, iUPD results from any significant further growth of non-target lesions, taken as a whole.

- New lesions
  - o New lesions appear for the first time
  - o Additional new lesions appear
  - o Previously identified new target lesions show an increase of  $\geq 5$  mm in the new lesion sum of diameters, from the nadir value of that sum
  - o Previously identified non-target lesions show any significant growth

If any of the events above occur, the overall response for that visit is iUPD, and the iUPD evaluation process (see Assessment at the Confirmatory Imaging above) is repeated. Progression must be confirmed before iCPD can occur.

The decision process is identical to the iUPD confirmation process for the initial PD, with one exception: if new lesions occurred at a prior instance of iUPD, and at the confirmatory imaging the burden of new lesions has increased from its smallest value (for new target lesions, the sum of diameters is  $\geq 5$  mm increased from its nadir), then iUPD cannot resolve to iSD or iPR. It will remain iUPD until either a decrease in the new lesion burden allows resolution to iSD or iPR, or until a confirmatory factor causes iCPD.

Additional details about iRECIST are provided in the iRECIST publication [Seymour, L., et al 2017].

CCI

CCI

CCI

CCI

CCI

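### Appendix 8 reclassifies progression called on new or non-target lesions as iSD or iPR when those lesions merely persist unchanged, and no iRECIST endpoint rule in Section 10 corrects for it

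*Combined protocol and SAP*

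**What the plan says.** Appendix 8 (Section 12.8) lists three ways to reach RECIST 1.1 progression: growth of target lesions, unequivocal progression of non-target lesions, and new lesions. The first such visit is read as iUPD "regardless of which factors caused the progression".

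At the confirmatory scan, progression is confirmed (iCPD) if a triggering factor worsens or a new progression factor appears. Otherwise two paragraphs apply:

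- **Persistent iUPD** requires that nothing has confirmed progression and that a second condition is met as well: "The target lesion sum of diameters (initial target lesions) remains above the initial PD threshold (by RECIST 1.1".
- **Resolution of iUPD** again needs no confirming factor, together with "The target lesion sum of diameters (initial target lesions) is not above the initial PD threshold". The reading is then iSD or iPR according to the target sum; only iCR needs every lesion to be gone. The appendix then draws this consequence: "the initial iUPD is considered to be pseudo-progression, and the level of suspicion for progression is “reset". A later progression therefore has to be confirmed from the start.

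The paragraph on visits after pseudo-progression adds one bar for later episodes. If new lesions were present at a prior iUPD and their burden has increased from its smallest value, "then iUPD cannot resolve to iSD or iPR".

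ORR and PFS by iRECIST are tertiary/exploratory (Section 4; Section 5.4.1.1). Section 10, including Table 11, derives ORR and PFS by RECIST 1.1 only.

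**The concern.** The entry rule and the exit rule do not match. Three kinds of finding can start iUPD, but once confirmation is excluded, only one of them (the sum of the initial target lesions) decides whether iUPD continues. Neither paragraph asks whether the new lesion or non-target progression that caused iUPD is still there. A participant can therefore be recorded as having had pseudo-progression while the lesion that caused the call is unchanged.

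At stake is the meaning of the exploratory iRECIST endpoints. With no iRECIST derivation in Section 10, Appendix 8 is their only definition. An iPR obtained this way could count as a response, and the reset could move a progression event to a later date.

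**Working it through.** The plan gives no figure on this point, so there is nothing to reproduce. The check applies the stated rule to each case.

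**Inputs.** Triggers, confirming factors, persistence and resolution rules, and the PD threshold (at least 20% and at least 5 mm above nadir) are from Appendix 8. Arm caps of about 25 (three smaller biomarker groups) and about 40 (high GEP, high TMB) are from Section 10.7. Scan timing is from Section 9.2.1.2.

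**Step 1: enumerate.** The triggering finding persists unchanged and no confirming factor is present.

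| Trigger of iUPD | Target sum above PD threshold | Below threshold, not PR | At PR level |
|---|---|---|---|
| Target lesions | iUPD | not applicable | not applicable |
| Non-target lesions | iUPD | iSD | iPR |
| New lesion | iUPD | iSD | iPR |

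In four of the seven possible cases the participant leaves iUPD although the trigger has not resolved. These are all the non-target and new-lesion cases with the target sum below the threshold.

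**Step 2: one case in numbers (illustrative).** A measurable new lesion, followed as a new target lesion, is 12 mm at iUPD and 14 mm at confirmation. The initial targets are 10% below baseline at both scans and were never lower.

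- New-lesion growth: 14 − 12 = 2 mm, under the 5 mm needed to confirm. No additional lesion appears, so the reading is not iCPD.
- Target sum: 0% above nadir, so it is not above the threshold and persistent iUPD is unavailable.
- Result: iSD and a reset. With targets at PR level and the rest unchanged, the result would be iPR.

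The case depends on the lesion being selected as a new target lesion. If it were followed as non-target, visible growth would confirm progression.

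**Step 3: does the later bar prevent this?** No. It needs a later iUPD episode and an increase in new-lesion burden (at least 5 mm above nadir for new target lesions). An unchanged lesion fails the second condition and a first episode fails the first. The same paragraph also provides for the case "If non-target lesions have shown previous unequivocal progression, and this progression has not resolved". It is written for visits after iUPD has been declared resolved, so the appendix itself foresees resolution with non-target progression still present.

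**Step 4: ORR.** Let k be the number of participants in an arm of size n whose only response is an iPR reached this way, and assume that it counts as a response. The rise in ORR is 100 × k/n.

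| Assumed k | n = 25 | n = 40 |
|---|---|---|
| 1 | 4.0 points | 2.5 points |
| 2 | 8.0 points | 5.0 points |
| 3 | 12.0 points | 7.5 points |

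The documents give no basis for k. Cases read as iSD add nothing.

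**Step 5: PFS.** The effect depends on an event date that the plan does not define.

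- Dated at first iUPD: no effect.
- Dated at the iUPD that is later confirmed: the reset discards the first iUPD, so the date moves to a later one.
- Dated at iCPD: later worsening starts a new iUPD that must itself be confirmed, so the event can come later.

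The direction is therefore upward or nil.

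**The case against.** The strongest reply is that the appendix is a complete set of outcomes: confirmed, still unconfirmed, or resolved. Confirmation is sensitive to non-target growth, visible growth of new non-target lesions and additional new lesions, so the target sum decides only after all of these are excluded. Unresolved non-target progression is foreseen, and further significant growth starts iUPD again. All of this stands, but it does not answer the point: unchanged progression is labelled resolved.

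Four stronger readings are tempting and should be set aside.

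- A reader might infer that iRECIST ORR and PFS are both inflated. ORR rises only through an iPR with no earlier response, and the case in Step 2 is iSD. PFS is unaffected under one of the possible event dates.
- A reader might infer that first and later iUPD episodes are handled inconsistently. For an unchanged lesion they are not, because the later bar covers only increased burden. At a first episode, new-lesion growth of 5 mm or more from the iUPD scan already confirms progression.
- A reader might infer a biased comparison of iRECIST with RECIST 1.1. Section 4 states no such comparison.
- A reader might estimate the share of progression events reclassified by multiplying assumed rates. The documents supply none. Many progressions may also have no confirmatory scan: clinically unstable participants need none (Section 9.2.1.5), and imaging is not required after discontinuation for documented progression (Section 9.2.1.3).

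Whether the rule departs from the published iRECIST criteria cannot be judged from these documents, and no such claim is made.

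**Conclusion.** The point holds as a defect of classification with limited reach. Followed as written, Appendix 8 turns unchanged new-lesion or non-target progression, with targets below the PD threshold, into iSD or iPR and resets the confirmation process.

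The possible effect is an upward bias in exploratory iRECIST ORR of 4.0 points (arm of 25) or 2.5 points (arm of 40) per affected participant, and an upward or nil effect on iRECIST PFS. These sizes assume arms at their caps and, for ORR, no earlier response. The number of affected participants is unknown.

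The primary ORR and secondary PFS are untouched because both use RECIST 1.1 (Sections 9.2.1.4, 10.4.1 and 10.6.1.2). The interim analyses use the primary ORR (Section 10.7) and are untouched too. This is a minor point, but worth settling before the exploratory results are derived.

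**What to change.** For the exploratory iRECIST endpoints only, add a derivation to Section 10 or the supplemental SAP that:

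1. keeps the category at iUPD while the non-target progression or new lesion that caused it persists without qualifying worsening;
2. counts iSD or iPR after iUPD only once that factor has regressed or disappeared;
3. dates the iRECIST PFS event at the first iUPD that is later confirmed without such resolution in between.

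Confined to derivation, this costs wording and programming and needs no additional scans. The downside is that the derived category may differ from the category the site recorded under Appendix 8.

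Appendix 8 also guides treatment, and Table 9 ties persistent iUPD to repeat imaging at 4 to 8 weeks while iSD, iPR and iCR return to the regular schedule. Any change to the appendix itself could therefore affect treatment or imaging. The clinical team must reconcile Appendix 8 with Table 9 on those matters; no change to either is proposed here.
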